In regard to organ motion, the largest motion of abdominal tumors and organs is caused by breathing, which complicates the planning process and affects the accuracy of radiation delivery. The American Association of Physics in Medicine (AAPM) Task Group 76 has recommended several methods to manage respiratory motion, and also recommended that respiratory management methods be considered if target motion is greater than 5 mm, or if normal tissue sparing is gained[1]. These methods include motion-encompassing methods, motion reduction methods and real-time tumor tracking methods. Motion-encompassing methods apply a motion margin to the targets to account for respiratory motion, resulting in excess normal tissue being irradiated. Current motion reduction methods use either breath-hold techniques or forced shallow breathing with abdominal compression. Real-time tumor tracking methods involve complicated techniques to detect the motion and dynamically reposition the radiation beam to follow tumor motions. Currently, there are no standard or best motion management options for all patients. However, motion reduction techniques may be simpler ways to address the motion issue while minimizing the injury to normal tissues. Current techniques to reduce the respiratory motion require either patient cooperation for breath-hold or abdominal compression, which may increase discomfort.

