4.3.5 Methodology Development to Create Pseudo-MRI from CBCT and Its Evaluation

CBCT has a limitation in differentiating targets from normal tissues. To better visualize targets and soft tissues, the method to synthesize MRI will be explored. The proposed method will use planning MRI images and their associated pseudo-CT images as well as CBCT images. First, CBCT is registered to pseudo-CT using rigid or deformable registration. Second, the transformation information from the previous registration is applied to the planning MRI to generate a synthetic CBCT-based MRI for target localization and alignment during treatment. To evaluate the quality of pseudo-MRI in target localization and alignment, the alignment using pseudo-MRI and planning CT will be compared with the alignment using CBCT and planning CT.

4.3.6 Study of the Potential Role of 4D-MRI in Treatment Planning and Image Guidance

4D-CT is usually acquired for motion assessment and management when treating tumors in chest and abdomen. When contouring target volumes, internal target volume (ITV) is defined based on the 4D-CT dataset in order to account for target motion. For abdominal tumors, it is challenging to directly assess target motion on 4D-CT without contrast administration or implantation of fiducial

markers. Thus, replacement of 4D-CT with 4D-MRI would be a beneficial step for motion assessment and an important part in the MRI-alone workflow for abdominal radiotherapy. To investigate the role of 4D-MRI in treatment planning, ITVs contoured using 4D-CT and 4D-MRI will be compared, and their dosimetric impact will be also evaluated.

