5 STATISTICAL CONSIDERATIONS

5.1 Statistical Considerations for Specific Aim 1

The primary clinical end point of specific aim 1 is to show the non-inferiority of the 4D-MR only workflow for ITV definition to that using 4D-CT. In the case of lung cancer Ehler et al. [20] have found using 4D-CT that different methodologies for the definition of the ITV yielded differences in ITV definition ranging from 1.7% to 43% with an average difference between methodologies of 17.5%. The observed differences in volume definition were confined to the periphery of the ITV volume. Therefore a difference of no larger than 14% between the ITV defined using our proposed 4D MR workflow versus 4D CT is considered as not being clinically meaningful. Based on the literature assuming a standard deviation of 16.3% and a non-inferiority margin of 14% in ITV volume definition between 4D-MR and 4D-CT, we find that if there is truly no difference between the ITV definition using 4D-CT and the ITV definition using 4D-MR. A sample size of 21 patients will achieve a 91% power to detect the non-inferiority using a one sided t-test and the true difference between the mean is 0. at a type 1 error rate of 0.01.

5.2 Statistical Considerations for Specific Aim 2

Using a conventional motion reduction technique employing an abdominal compression pillow we have found an average motion reduction of 12% with a standard deviation of 13% for lesions within the lung [21]. Achievable motion reduction ranged from 3% to 28%, therefore an average motion reduction of at least 12% with CPAP is considered clinically meaningful. Using pairwise analysis assuming a mean difference of 12% between free breathing and the application of CPAP with an associated standard deviation of 13%, and an $\alpha=0.01$, using a two sided paired t-test we find that with 21 patients will have 90% power to detect a motion reduction of at least 12% when using CPAP. Assuming an allocation ratio of 1:1 between the two arms of this study we are planning to recruit a maximum of 42 patients to this study, however once, 21 patients have been

accrued to the CPAP arm no further patients will be enrolled into that part of the study and the study will be closed once the necessary patient number for aim 1 has been achieved.

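### Aim 1 tests an unsigned 14% ITV limit with a single one-sided t-test and never says whether a larger or a smaller 4D-MR ITV is the inferior result

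*Combined protocol and SAP*

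**What the plan says.** Section 5.1 defines the primary endpoint of Aim 1 as an attempt to "show the non-inferiority of the 4D-MR only workflow for ITV definition to that using 4D-CT". The clinical limit is "a difference of no larger than 14% between the ITV defined using our proposed 4D MR workflow versus 4D CT", given without a sign. It is derived from published lung data showing "differences in ITV definition ranging from 1.7% to 43% with an average difference between methodologies of 17.5" percent, also without signs.

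The calculation proceeds by "assuming a standard deviation of 16.3% and a non-inferiority margin of 14% in ITV volume definition between 4D-MR and 4D-CT", with a true mean difference of 0 and a type 1 error rate of 0.01. It concludes: "A sample size of 21 patients will achieve a 91% power to detect the non-inferiority using a one sided t-test".

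The section does not state how the difference is signed, which null hypothesis is tested, or which direction is inferior. Section 4.3.6 adds only that "ITVs contoured using 4D-CT and 4D-MRI will be compared, and their dosimetric impact will be also evaluated". It sets no direction and no success rule.

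**The concern.** A non-inferiority test needs a named bad direction, and a volume does not supply one. The protocol itself gives a reason to care about each side. Section 4.3.6 says that the "internal target volume (ITV) is defined based on the 4D-CT dataset in order to account for target motion", so an ITV that is too small may fail to cover the motion. Section 2.1 notes that "Motion-encompassing methods apply a motion margin to the targets to account for respiratory motion, resulting in excess normal tissue being irradiated", so an ITV that is too large also has a cost.

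Two consequences follow. First, whichever side is tested, a mean difference beyond the plan's own 14% on the other side does not count against success. Second, because no side is fixed in advance, nothing in the text prevents the side from being settled once the results are known, and the type 1 error of 0.01 would then not be protected.

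Section 4.3.2 has patients treated on CT-based plans, so their treatment does not depend on this test. What is at stake is the conclusion that 4D-MRI can replace 4D-CT for ITV definition.

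**Working it through.** **Inputs (section 5.1).** n = 21, SD = 16.3%, margin = 14%, one-sided alpha = 0.01, true difference 0. Assumption: 16.3% is the SD of signed paired percentage differences (4D-MR minus 4D-CT). The document does not say so, but the paired formula is the one that reproduces its power.

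**Step 1: reproduce the stated power.** Standard error = 16.3/√21 = 3.557. Noncentrality = 14/3.557 = 3.936. Critical value t(0.99, 20 df) = 2.528. The noncentral t gives power 0.909, matching the stated 91%. A two-sample t-test with 21 per group gives 0.641, and a paired test at 0.005 gives 0.848. The stated figure is therefore the power of one paired one-sided test.

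**Step 2: power for the unsigned limit.** TOST requires both mean + 2.528·s/√21 < 14 and mean − 2.528·s/√21 > −14, where s is the sample SD. Integrating over the distribution of s, with a true difference of 0:

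| SD (%) | One-sided power | TOST power |
|---|---|---|
| 15 | 95.1% | 90.2% |
| 16.3 | 90.9% | 81.9% |
| 20 | 74.6% | 49.8% |

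**Step 3: a true shift on the untested side.** If only the upper limit is tested and the true mean is −14%, the distance to the limit is 28 points and the noncentrality is 28/3.557 = 7.872. Pass probabilities at n = 21:

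| SD (%) | One-sided, 14% shift | One-sided, 20% shift |
|---|---|---|
| 16.3 | >99.99% | >99.99% |
| 25 | 99.3% | 99.97% |
| 30 | 95.1% | 99.4% |
| 40 | 74.6% | 90.3% |

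At SD 16.3, TOST passes 1.0% of the time at a 14% shift and 0.005% at 20%. The SDs above 16.3 are sensitivity values, not document figures.

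**Step 4: side chosen after the data.** The upper test passes if mean < 14 − 2.528·s/√21. The lower test passes if mean > −14 + 2.528·s/√21. Together they cover every possible mean when s < 14·√21/2.528 = 25.38. At a true SD of 16.3, P(s < 25.38) = 0.9996.

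The probability that at least one test passes is lowest at a true difference of 0, where it equals 2 × one-sided power − TOST power:
- SD 16.3: 2 × 0.90933 − 0.81870 = 0.99997
- SD 20: 2 × 0.74594 − 0.49756 = 0.9943
- SD 25: 2 × 0.52635 − 0.14914 = 0.9036

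Simulation at SD 16.3 agrees, with either side passing in more than 99.99% of runs and both in about 82%.

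**Step 5: could the endpoint be the absolute difference?** One upper-side test would then cover both directions. But the plan assumes a mean difference of 0 with SD 16.3%, and an absolute difference with mean 0 must have SD 0. That reading does not fit.

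**The case against.** The strongest reply is that non-inferiority is one-sided by definition. Section 5.1 uses that term throughout, never refers to equivalence, and pairs it with a matching one-sided test and a correct power figure. Every non-inferiority test passes a large shift in the favourable direction. On this view the defect is one missing sentence on sign and direction, and the symmetric reading of the 14% is reasonable but not forced. This stands in part: naming and justifying a direction would be a legitimate repair and would keep the 91%. It does not rescue the present text, because no favourable direction is given and the protocol's own reasoning points both ways.

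Second, nothing in the document suggests that anyone means to pick the side afterwards. That is right. Step 4 shows what the wording permits, not a planned procedure. The unprotected side remains even if a direction is fixed in good faith.

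Third, the ITV comparison and dosimetric evaluation in section 4.3.6 would make a material shift visible. They would do so descriptively, with no bearing on declared success.

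Fourth, the TOST power is fragile. The literature differences are all positive, so 16.3% might describe magnitudes. Purely as an assumption, if magnitudes had mean 17.5 and SD 16.3 and signed differences centred on 0, the signed SD would be √(17.5² + 16.3²) = 23.9. TOST power would then be about 20% and one-sided power about 57%. This stands as a caution on the 82%. It weakens the plan's 91% as well, and it does not supply the missing direction.

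**Conclusion.** The concern holds and needs correction before analysis, because it affects the primary endpoint of Aim 1. Neither the sample size of 21 nor the 91% is miscalculated for a single one-sided paired test. The fault is that this test guards only one side of a limit stated without a sign, and the side is not named.

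At the planned SD, a 4D-MR ITV that breaches the 14% limit on the untested side would almost always be declared non-inferior. Power for the limit as worded is about 82%, not 91%. The pass rate on the untested side stays high across a wide range of SDs. The TOST power depends much more on the SD and on the unconfirmed assumption that 16.3% describes signed paired differences.

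**What to change.** Amend section 5.1 before analysis in one of two ways.

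1. **Bound both sides.** Define the endpoint as the mean signed paired percentage ITV difference (4D-MR minus 4D-CT). Require its 98% confidence interval to lie within -14% to +14%, which is TOST at 0.01 per side. Restate power as about 82% at n = 21, with the SD assumption made explicit (90% at SD 15, 50% at SD 20).
2. **Keep one side.** Name the inferior direction, justify leaving the other side untested, and limit the conclusion to that direction. The 91% then stands.

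Both are wording changes and neither requires more patients. Option 1 costs about 9 points of stated power. If at least 90% is wanted under option 1, 25 patients give 91.4% (24 give 89.6%), which is within the 42-patient maximum. Section 5 should then also say whether both arms count toward the Aim 1 number. Option 2 costs nothing in power but supports a narrower claim, with no protection on the other side.

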6 EXPECTED ADVERSE EVENTS

6.1 MRI Scans

MRI Scan:
Anxiety/Stress
Claustrophobia
Discomfort

Gadolinium:
Allergic reaction to contrast agent
Headache
Nausea
Vomiting
Rash
Temporary low blood pressure
Nephrogenic Systemic Fibrosis (NSF)/Nephrogenic Fibrosing Dermopathy (NFD).

NOTE: Precautions should be exercised for patients with a history of grand mal seizures, severely impaired renal function or hemolytic anemia. The very unlikely possibility of a reaction, including anaphylactic or cardiovascular reactions, should be considered especially for patients with a known sensitivity to Gadolinium or history of asthma. Nephrogenic Systemic Fibrosis (NSF) or Nephrogenic Fibrosing Dermopathy (NFD) (kidney disorders), may occur in patients with moderate to end-stage kidney disease after they have had a MRI scan with gadolinium-based contrast agent.

Needle Placement:
Minor discomfort;
Bleeding;
Infection;
Bruising.

6.2 CPAP

CPAP is a safe form of therapy with relatively few recorded major complications. Hypotension, local skin irritation, drying of the nasal and pharyngeal membranes, nasal congestion/rhinorrhea, gastric distention, vomiting, and eye irritation are the rare adverse events. Nevertheless, minor discomfort and complaints regarding the mask interface remain relatively common[15].

7 PROTECTION OF HUMAN SUBJECTS FROM RESEARCH RISK

7.1 Human Subjects Involvement and Characteristics

We expect to enroll a maximum of 47 subjects (42 patients + 5 healthy volunteer subjects) over a 24-month period. For each patient participating in the study, the research will involve a pretreatment MRI and CT scans and treatment CBCT and orthogonal kV/MV images as described in Section 3. No patients will be excluded based on racial/ethnic or sex/gender.

7.2 Source of Materials

The source of data consists of CT, MRI, CBCT and orthogonal kV/MV images and treatment plans as described in Section 3. A data record will be kept in a locked cabinet in the project leader's office, which will be accessible only to the scientific staff involved with this research project.

7.3 Potential Risks and Protection against Risks

The MRI scans are minimally invasive. The only contraindications to a MRI scan are the presence of any ferrous metal in the body or claustrophobia. Prior to arriving at the MRI facility, all patients will be required to complete a standard clinical screening form for any metallic implants or ferrous material they may have in their bodies. Any presence of such material will immediately disqualify them from the study.

CPAP is a safe form of therapy with rare complications. Relative contraindications include patients with bullous lung disease, fibrotic lung disease, Claustrophobia and recurrent sinus or ear infections. The absolute contraindications include obtundation /unconsciousness, chest wall trauma, suspected pneumothorax, persistent nausea/vomiting, active upper GI bleeding, history of recent gastric surgery, facial anomalies/trauma. All patients will be required to complete a screening form for any of these histories. Any presence of these histories will immediately disqualify them from Arm 2 protocol. If there is any question about the above history and medical problems, the patient will be referred to a pulmonologist for consultation.

7.4 Recruitment and Informed Consent

Drs. [name], [name], [name], and [name] will recruit patients for this study, and [name] will evaluate if patients are eligible to be enrolled in Arm 2 CPAP protocol. The patients who participate in the study will be screened, educated, and consented. Most imaging protocols described in this research proposal are routine clinical imaging protocols in use at our institution. Imaging sequences that usually are not used in abdominal scans will be optimized and tested on volunteers before using them in patients who participate in the study (Refer to Section 4.3.3).

8 DATA AND SAFETY MONITORING PLAN

Adverse events will be collected and reported according to a DSMP described in Appendix I.

APPENDIX I

OVERSIGHT AND MONITORING PLAN

The Albert Einstein College of Medicine/Albert Einstein Cancer Center Data Safety Monitoring Committee (DSMC) has the responsibility for ensuring data and safety monitoring along with the PI who is ultimately responsible for the ongoing monitoring and safety of clinical protocols. The primary functions of the AECC DSMC are as follows:

1. To review and ensure protocol compliance with dose escalation in phase I trials
2. To review/assure protocol compliance for all trials that have two-stage phase II designs,
3. Reviewing all internal and external serious adverse reports, investigator alerts, action letters, and other safety reports for trials being performed at AECC-affiliated institutions and;

To implement and to determine the adequacy of DSM plans of all approved protocols.

The DSMC is an independent committee and meets on a monthly basis. During its monthly meeting, the DSMC will review serious adverse events from this study. In the event that the DSMC decides that a revision is warranted, the committee will immediately notify the principal investigator of this study. The DSMC has the authority to close trials to patient accrual should the risk to patients be excessive or outweigh the potential benefits of the study. All study suspensions and closures will be forwarded to the IRB/CCI and study sponsor from the DSMC.

MONITORING AND REPORTING GUIDELINES

An adverse event can occur on any clinical trial; it is the responsibility of the PI and the research team to identify, review, and report all necessary adverse events to the institutional IRB, the sponsor, and governmental agencies (i.e., NCI and/or FDA) as appropriate. Adverse events should be identified through standard, routine protocol review and clinical assessment of each subject participating in the clinical trial. This review should be timely in order to meet the requirements for adverse event reporting defined below:

Adverse Event (AE)

An adverse event is defined by the GCP (Good Clinical Practice guidelines) as an undesirable experience occurring to a subject during a clinical trial, whether or not considered related to the investigational products.

Serious Adverse Event (SAE)

A serious adverse event is an adverse experience that fits one or more of the conditions noted below:

1. Fatal or life threatening
2. Disabling
3. Results in hospitalization or prolongation of hospitalization
4. Results in a congenital anomaly or occurrence of malignancy

All Serious Adverse Events, regardless if they are unrelated to study treatment, should be reported to the IRB and sponsors. These include, but may not be limited to:

1. All deaths
2. All SAE associated with study procedures
3. Any serious problem
4. Any recurring problem
5. Any outside AE report
6. Any unanticipated side effects

Unexpected Adverse Event

An unexpected AE is an experience not previously reported (in nature, severity, or incidence) in the current Investigator's Brochure or protocol document.

EXPEDITED REPORTING OF ADVERSE EVENTS

Depending on the nature, severity, and attribution of the event an ADR report will be phoned in, submitted in writing, or both according to the table below. Telephoned Adverse Events must also be reported by email to the AECC DSMC within one working day of the event. All adverse events must also be reported to the Montefiore Medical Center IRB, and any sponsor/funding agency not already included in the list.

Telephone reports to:

Study Co-Chair: [name]
[contact]
[contact]

Written reports to:

[name], MMC IRB
[contact]

MMC IRB – Copy of final written report to Sponsor.

EXPEDITED REPORTING TABLE

Summary of Reporting Requirements for Adverse Events	
Expedited Reporting	
Unexpected Events	
GRADES 2 and 3 Attribution of possible, probably or definite	GRADES 4 and 5 Regardless of attribution
Expedited report within 15 working days to FDA (Grade 1 – Adverse Event Expedited Reporting NOT required)	Report by phone to FDA within 24 hours. Expedited report to follow within 15 working days. This includes all deaths within 30 days of the last dose of treatment with an investigational agent regardless of attribution. Any late death attributed to the agent (possible, probable, or definite) should be reported within 15 working days.

For Hospitalization Only – Any medical event equivalent to the CTC Grade 3, 4, 5 which precipitated hospitalization (or prolongation of existing hospitalization) must be reported regardless of requirements for phase of study, expected or unexpected and attribution.

Expedited reporting may not be appropriate for specific expected events for certain later phase 2 and phase 3 protocols. In those situations the adverse events that will not have expedited reporting must be specified in the text of the approved protocol. An expected grade 3 event that is using the generic reporting criteria, for instance. In a trial of investigational agents where grade 3 diarrhea requiring hospitalization is expected, only diarrhea requiring ICU care (grade 4) might be designated for expedited reporting.
